1. PROTOCOL SUMMARY

1.1 Schedule of Activities (SoA)

The procedures for the screening and treatment periods in this study are presented in Table 1.

For olaparib treatment

- Patients may delay dosing under certain circumstances
 - Dosing may be delayed per the Dosing Modification and Toxicity Management Guidelines (see section 8.4.5) due to adverse events (AE)
 - If dosing must be delayed for reasons other than treatment-related toxicity, dosing will resume as soon as feasible.
 - In the event that olaparib is discontinued or delayed as part of the toxicity management guidance, TMZ may still be administered as scheduled.

For Temozolomide (TMZ) treatment

- Dosing may be delayed per the Dosing Modification and Toxicity Management Guidelines (see section 8.4.5) due to AEs.
 - If dosing must be delayed for reasons other than treatment-related toxicity, dosing will resume as soon as feasible.
 - In the event that TMZ is discontinued or delayed as part of the toxicity management guidance, olaparib may still be administered as scheduled.

Table 1 Schedule of Activities

Tests	Screening	Treatment Period (Each cycle repeats every 21 days)										End of Treatment ^a	Safety Follow-up ^m	Long Term Follow-up ^b		
		Cycle 1			Cycle 2		Cycle 3		Cycle 4		Cycle 5 and beyond					
		Day -28 to -1	D1 ± 3 days	D8 ± 3 days	D15 ± 3 days	D1 ± 3 days	D 15 ± 3 days	D1 ± 3 days	D15 ± 3 days	D1 ± 3 days	D15 ± 3 days	D1 ± 3 days				
Administrative Procedures																
Informed Consent	X															
Inclusion / Exclusion Criteria	X															
Demographics and Medical History	X															
Prior and Concomitant Medication Review	X	X	X	X	X	X	X	X	X	X	X	X	X			

Clinical Procedures / Assessments																
Review Adverse Events	X	X	X	X	X	X	X	X	X	X	X			X	X	X
Full Physical Examination	X	X												X		
Directed Physical Examination			X	X	X	X	X	X	X	X	X			X		
Vital Signs and Weight ^c	X	X	X	X	X	X	X	X	X	X	X		X	X		
ECOG PS ^d	X	X	X	X	X	X	X	X	X	X	X		X	X		
Post Study Anti-cancer Therapy Status													X	X	X	
Adverse Event Recording		X												X	X	
Long Term Follow-Up																X
SAE Recording		X												X	X	X
Treatment / Supportive Care Administration																
Olaparib		Continuous administration ^e														

Temozolomide		X ^e			X ^e		X ^e		X ^e		X ^e				
Laboratory Procedures / Assessments															
Pregnancy Test	X ^f	X ^f			X ^f		X ^f		X ^f		X ^f				
Clinical chemistry ^o	X	X ^g	X ^g	X ^g	X ^g		X ^g		X ^g		X ^g		X		
CBC with differential	X	X ^g	X ^g	X ^g	X ^g		X ^g		X ^g		X ^g		X		
PT/INR and aPTT ^p	X														
Urinalysis	X	X													
CEA	X	X			X		X		X		X				
TSH	X ^h								X ^m						
EKG	X ⁿ														
Efficacy Measurement / Imaging															
CT Chest / Abdomen / Pelvis	X ⁱ	Response assessment imaging will be performed every 6 weeks (+/3 days) ^j										X ^k		X ^k	
Tumor Biopsies/Correlative Studies Blood															
Biopsy ^l	X												X		

Research Blood collection	X ^r	X	X	X	X		X		X				X	X	
Stool Sample	X ^q						X ^q								

a. An end of treatment visit will be done within 7 days after progression of disease or discontinuation of study treatment for other reasons, and an additional follow up visit at 30 ± 7 days post discontinuation. In the case that the patient initiates a subsequent anti-cancer therapy, the 30 day follow up should occur prior to the first dose of the new therapy and the patient will move to long term follow up.
 
b. After the end of treatment visits the subjects will enter long-term follow up during which information on survival and subsequent anticancer therapy will be obtained by phone every 12 weeks until the subject dies, is lost to follow up, or withdraws consent. Patients who come off study for reasons other than disease progression should be assessed in the clinic and radiographically every 6 weeks (± 7 days) for the first year and 12 weeks (± 7 days) after the first year.
 
c. Vital signs should include temperature, pulse, respiratory rate, weight and blood pressure. Height will be measured on day 1 only. For cycles 2 and beyond, vital signs may be performed up to 2 days before Days 1 and/or 15.
 
d. For treatment cycles 2 and beyond, physical examination, ECOG performance status, weight/BSA may be performed up to 2 days before Days 1 and/or 15.
 
e. Olaparib will be taken continuously at a starting dose of 150 mg twice daily on days 1-21; Temozolomide will be taken days 1-7 every 21 days at a starting dose of 75 mg/m².
 
f. A pregnancy test at screening and on Day 1 is only required for women of “child bearing potential” as defined in the inclusion criteria. If required, the pregnancy test prior to cycle 1 may be done up to 72 hours prior to the treatment of study medications. A pregnancy test is required on day 1 for each cycle (+/- 72 hours) for women of “child bearing potential.”
 
g. For cycle 1 pre-treatment labs should be drawn within 24 hours prior to study treatment. After cycle 1, pre-treatment labs can be drawn up to 72 hours pre-dose.
 
h. TSH (reflex T3, FT4) will be drawn at screening and prior to treatment with cycle 4, and every 4 cycles thereafter (i.e. cycle 8, cycle 12, cycle 16, etc...)
 
i. A baseline CT scan will be done – 28 to -1 days prior to study treatment.
															

- j. Response assessment CT scans will be performed at the end of cycle 2 and at the end of every subsequent second treatment cycle at day 18 +/- 3 days (i.e. Days 15 to 21 of cycles 2, 4, 6, 8 and beyond). After 12 cycles, if disease is stable or improving, imaging will be performed in the same manner after every third cycle.
- k. Patients who come off study for reasons other than disease progression will continue to undergo a CT Chest / Abdomen / Pelvis every 6 weeks (\pm 7 days) for the first year and every 12 weeks (\pm 7 days) after 1 year.
- l. A mandatory pre-treatment biopsy will be required for all patients if deemed to be low risk and safe in the opinion of the treating investigator. An optional treatment biopsy after disease progression will also be obtained.
- m. A safety follow up visit will be scheduled 30 days \pm 7 days post discontinuation. If the patient is to start a new therapeutic agent prior to this 30-day period, the safety follow up visit must take place before the subsequent agent is given. Follow up visits will then be every 8 weeks post discontinuation.
- n. An EKG will be done at screening and as clinically indicated while on study. If abnormalities on EKG are noted an echocardiogram maybe performed as clinically indicated.
- o. Refer to section 8.2.1 for specific laboratory variables to be drawn.
- p. Patients who are taking warfarin may participate in this trial; however, it is recommended that INR be monitored carefully at least once per week for the first month, then monthly if the INR is stable.
- q. Refer to the lab manual for stool collection instructions.
- r. For patients undergoing tumor biopsy and patient derived xenograft generation, 2 additional research tubes may be collected during screening around the time of biopsy as outlined in the lab manual.

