Data from studies of olaparib in combination with various chemotherapy agents indicate an increase in bone marrow toxicity (anaemia, neutropenia, thrombocytopenia) greater than expected if the agents had been administered alone. The effects are generally transient but treatment delays are common and alternative administration schedules/toxicity management processes are currently being evaluated within some of these studies. When this type of toxicity has occurred it has been managed by routine clinical practice including dose delays, dose reductions, intermittent dosing and/or the use of supportive care measures, including G-CSF. Currently, all ongoing olaparib combination studies are being closely monitored for myelotoxicity. Results of a Phase II study in combination with carboplatin/paclitaxel (Study D0810C00041) showed that addition of olaparib to carboplatin AUC 4 + paclitaxel in the chemotherapy phase had a generally similar tolerability profile to carboplatin AUC 6 + paclitaxel. The regimen of olaparib capsules 200 mg bd for 10 days out of 21, with carboplatin AUC 4 + paclitaxel had an acceptable and manageable tolerability profile in patients with recurrent serous ovarian cancer. Olaparib tolerability during the monotherapy maintenance phase was consistent with the previously known safety and tolerability profile. In Study D0810C00039 and Study D081BC00004, olaparib 100 mg tablet bd in combination with weekly paclitaxel 80 mg/m² was well tolerated, with no new unexpected safety findings. In both studies, the incidence of neutropenia was higher for the olaparib combination arm and this contributed to higher rates of dose modifications for patients on olaparib compared to placebo. In Study D081BC00004, there was also a higher incidence of anaemia on the olaparib + paclitaxel combination arm than on the placebo + paclitaxel arm and more dose interruptions, reductions and discontinuations.

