8.4.5 Management of adverse events related to Olaparib and TMZ

Any toxicity observed during the course of the study could be managed by interruption of the dose of the attributed study treatment or dose reductions. Repeat dose interruptions are allowed as required, for a maximum of 4 weeks on each occasion. If the interruption is any longer, the study team must be informed. Olaparib treatment can be dose reduced to 100 mg twice daily. If the reduced dose of 100 mg twice daily is not tolerable, olaparib can be further dose reduced to 100 mg daily, and if this is not tolerable no further dose reduction is allowed and study treatment should be discontinued. Temozolomide can be dose reduced to 60 mg/m² (Days 1-7), and if this is not tolerable TMZ can be further dose reduced to 50 mg/m² (Days 1-7). The following tables should be applied if an AE is deemed to be at least “possibly related” to olaparib, TMZ, or both. If an AE is only attributed to one of the agents the other agent may be continue at an unadjusted dose.

Once dose is reduced, escalation is not permitted (except following concomitant treatment with CYP3A4 inhibitors – see Section 6.5

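### Table 1 sets response scans by calendar weeks and its footnote j sets them by treatment cycles; no section says which rule holds when dosing is delayed, so toxicity can set the timing of PFS assessments

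*Combined protocol and SAP*

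**What the plan says.** All of the scheduling text is in section 1.1. The imaging row of Table 1 reads "Response assessment imaging will be performed every 6 weeks", with a tolerance of about 3 days, and carries footnote j. Footnote j reads "Response assessment CT scans will be performed at the end of cycle 2 and at the end of every subsequent second treatment cycle". Its target is cycle day 18 with a tolerance of 3 days either way, which it spells out as "i.e. Days 15 to 21 of cycles 2, 4, 6, 8 and beyond". It then adds: "After 12 cycles, if disease is stable or improving, imaging will be performed in the same manner after every third cycle". Table 1 gives the cycle length: "Each cycle repeats every 21 days".

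On delays, section 1.1 states for each drug that "Dosing may be delayed per the Dosing Modification and Toxicity Management Guidelines", and lets either drug continue while the other is held. Section 8.4.5 says "Repeat dose interruptions are allowed as required, for a maximum of 4 weeks on each occasion". Section 2.3.1, on olaparib combined with various chemotherapy agents, says of marrow toxicity that "treatment delays are common". In section 8.4.5.1, Table 11 interrupts both drugs for haemoglobin below 8 g/dl, and Table 12 requires dose interruption for grade 3-4 low counts.

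Section 8.1.2 asks sites to keep to the planned imaging dates after an unscheduled scan. It does not mention dose delays. Footnote k puts patients who leave the study without progression on calendar scans, every 6 weeks in the first year and every 12 weeks after it.

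PFS is a secondary endpoint. Section 8.1.3 runs it from enrolment to radiological progression or death. Section 9.4.1 censors it at the last RECIST assessment and compares it across clinical measurements by Cox regression.

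**The concern.** Progression by imaging can be dated only at a scan, so the scan schedule is part of how PFS is measured. Under a calendar rule the spacing does not depend on treatment. Under a cycle rule it stretches whenever a hold pushes back the next cycle, and holds here are mainly for toxicity. Two patients with the same true progression date can then have different recorded dates because one had low counts.

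With both rules in the same table, site staff could follow either and be compliant, and the analyst could not tell afterwards which rule set a given date. What is at stake is the absolute PFS estimate, any comparison of it with historical PFS, and Cox comparisons by factors related to toxicity. The plan also treats patients unevenly within one endpoint: a patient who has left the study without progression is scanned by the calendar, while under footnote j a patient on a toxicity hold need not be.

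**Working it through.** **1. The plan's own interval.** Two cycles: 2 × 21 = 42 days = 6 weeks. Row and footnote agree if nothing slips. Day 18 falls on study day 21 + 18 = 39 in cycle 2, 63 + 18 = 81 in cycle 4 and 105 + 18 = 123 in cycle 6, all 42 days apart.

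**2. After cycle 12.** Three cycles: 3 × 21 = 63 days = 9 weeks, against 6 in the row. This difference needs no delay.

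**3. First-scan window, no delay.** Footnote j: study days 21 + 15 = 36 to 21 + 21 = 42. Row: 42 ± 3 = days 39 to 45, if the 6 weeks are counted from cycle 1 day 1. The row names no anchor, so that is an assumption. The windows overlap on days 39-42.

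**4. One hold, if footnote j governs and the hold moves the cycle start.** A 28-day hold before cycle 2 moves the first scan from day 39 to 39 + 28 = 67. A 28-day hold before cycle 3 stretches the first between-scan gap from 42 to 70 days (10 weeks). One such hold in each of two successive cycles within a gap gives 42 + 56 = 98 days (14 weeks), an extreme case.

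**5. Effect on recorded progression in affected patients.** Scan dates were generated from footnote j, with holds added before cycle starts. True PFS was taken as exponential with median 2, 3, 4 or 6 months; these are assumptions, since the documents give no PFS figure. Recorded progression is the first scan after true progression. Ranges run over the four medians, and each row is compared with no hold.

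| Hold | First three scans (day) | Mean shift (weeks) | Recorded later / earlier |
|---|---|---|---|
| none | 39, 81, 123 | 0 | – |
| 7 days before cycle 2 | 46, 88, 130 | 0.07-0.21 | 87% / 13% |
| 28 days before cycle 2 | 67, 109, 151 | 0.40-1.21 | 49-55% / 45-51% |
| 28 days before cycle 3 | 39, 109, 151 | 0.36-0.83 | 37-44% / 27-42% |
| 28 days before cycles 2 and 3 | 67, 137, 179 | 0.74-1.81 | 48-70% / 30-52% |
| 28 days in every scan interval | 67, 137, 207 | 2.04-2.28 | 63-70% / 24-26% |

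The shift differs in sign between patients because a hold moves every later scan. With 28 days before cycle 2, true progression on day 30 is recorded on day 67 instead of 39 (28 days later), but true progression on day 50 is recorded on day 67 instead of 81 (14 days earlier). The recorded median jumps between scan dates: under this hold it goes from day 81 to 67 for a true median of 2 months, and from day 123 to 151 for 4 months.

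**6. Effect averaged over a trial.** Assumptions: 200,000 exponential times with true median 10, 13 or 17 weeks, scans at the end of 6-week blocks, and a 1-4 week delay in 30% or 50% of blocks, assigned at random. The mean recorded time rises by about 0.5-0.9 weeks. For a true median of 13 weeks the recorded median falls, from 18.0 to about 17 weeks.

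**7. Primary endpoint.** The rule in section 9.2 (stop at 0 of 9; reject at 4 or more of 30) gives early stopping under the null of 0.95^9 = 0.630, expected size 9 + 0.370 × 21 = 16.8, alpha 0.0489 and power 0.902. The plan states 63%, 17, .049 and 90%. None of these uses the scan interval.

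**The case against.** The case for leaving the text alone has four parts.

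- **A footnote normally qualifies its row.** Footnote j can be read as the operative rule, and the wider interval after cycle 12 as a planned relaxation. That is fair, and without delay the footnote does give exactly 42 days through cycle 12. But reading it this way makes the cycle count govern, which is the reading under which holds move scans.
- **A hold need not move the cycle.** Either drug may continue while the other is delayed, olaparib is given continuously, and a hold that begins after the day 15-21 scan affects only the next one. This stands: postponement is conditional. It does not cover the expected marrow toxicity well, since Table 11 stops both drugs for severe anaemia.
- **The effect is small and rests on assumed inputs.** This also stands. The remark in section 2.3.1 about delays concerns other combinations and gives no rate for this regimen. Deaths without prior progression are unaffected.
- **PFS is secondary, in one arm, with no test against a benchmark.** Correct: there is no between-arm bias, and the go/no-go decision rests on response.

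A reader might go further and infer that 12-week PFS would be inflated by 7-12 percentage points, because the model in step 6 gives that. The figure is an artefact: week 12 is a scan date in the model, so any delay carries a week-12 record past the cut. In the same model the proportions recorded progression-free beyond weeks 11 and 16 fall, by about 2-5 points. The plan defines no 12-week PFS endpoint.

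**Conclusion.** The conflict between the row and footnote j is real, and nothing in the documents resolves it for dose delays. After cycle 12 the two differ, 9 weeks against 6, even without delay. If footnote j governs and a hold moves the cycle start, assessment timing depends on toxicity and recorded PFS is later on average: about 0.5-0.9 weeks across a trial under the step 6 assumptions, and from about 0.1 to just over 2 weeks in affected patients under the step 5 scenarios.

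A reader might infer that delays simply inflate PFS in the patients with most toxicity. The documents and the calculations do not support that. The documents state neither condition for postponement, the direction varies between patients, the recorded median can fall as well as rise, and delays were assigned at random in step 6, so no excess in a high-toxicity group was tested.

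The point is worth correcting because the correction is cheap and removes a dependence on toxicity from a reported endpoint. It does not touch the response-rate design.

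**What to change.** Rewrite the Table 1 row and footnote j as one rule: response scans fall due at fixed calendar weeks from cycle 1 day 1 (6, 12, 18 and so on), regardless of dose delays, with a single window used in both places. State the interval after the first 12 cycles in calendar weeks and reconcile it with the row. Extend the sentence in section 8.1.2 on keeping to the planned imaging dates so that it covers dose delays as well as unscheduled scans.

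If the sponsor prefers to keep cycle-based scans, state what a hold of one or both drugs does to the cycle count, and add a sensitivity analysis that treats progression times as interval-censored between scans.

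The cost is wording only. The practical downside is that some scans will fall during a dose hold and need separate booking.

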1.2 Synopsis

Principal Investigator

[name]
Yale Cancer Center
Yale School of Medicine
[name]
[name]
USA

Statistician

[name]
Yale School of Public Health
[name]
[name]
[name]
Office: [contact]
[contact]
[contact]

Protocol Title: Temozolomide and Olaparib for O⁶-Methylguanine DNA Methyltransferase Promoter Hypermethylated Colorectal Cancer

Short Title: TMZ + Olaparib for MGMT Hypermethylated Colorectal Cancer

Rationale:

Colon cancer is the third most common cancer in the United States, and it accounts for 9% of all cancer related deaths (Cronin et al. 2018). Systemic medical therapy is essential in management of these patients. Over the last two decades a number of available systemic treatments have improved both quality of life and overall survival, which now exceeds 2 years for stage IV disease (Loupakis et al. 2014a). However, the optimal sequence for the use of the available drugs is not clear and exposure of all of the active agents seem to be more important than the order of administration. Hence, the more lines of therapy we can offer to patients, the more benefit patients can derive in terms of their survival and quality of life. Effective biomarkers are lacking for CRC.

However, O⁶-methylguanine DNA methyltransferase (MGMT) promoter hypermethylation is described in up to 40% of colorectal adenocarcinoma in prospective studies as well as subsets of gastric, pancreatic, and neuroendocrine tumors where it has been associated with increased sensitivity to TMZ and dacarbazine (Thomas 2017, Bae 2002, Konduri 2009, Esteller 1999, Kulke 2009, Walter 2015). Promoter hypermethylation of MGMT is most widely described in glioma and when accompanied by CIMP, almost universally results in MGMT promoter methylation in these tumors (van den Bent 2013, Clark 2016, Noushmehr 2010, Turcan 2012). Promoter hypermethylation ultimately causes decreased MGMT expression and renders these tumors more susceptible to TMZ (Chinot 2007, Brandes 2006, Hegi 2005). The monofunctional

alkylator, TMZ causes three common types of alkylation DNA damage, which are depicted in Fig 2. The MGMT protein is the major pathway for the removal of 06-methylguanine lesions, which are extremely toxic in replicating cells and is frequently silenced by promoter hypermethylation in many cancers, either focally or as a result of CIMP. Additionally, a major mechanism for repair of N7-methylguanine and N3-methyladenine lesions is by base excision repair, which is blocked by treatment with PARP inhibitors.

Inhibitors of base excision repair and MGMT have been shown to sensitize tumors to TMZ (Delaney 2000, Trivedi 2005, Barvaux 2004, Hermisson 2006, Yan et al. 2007, Luo 2004, Liu et al. 2003). Tumor sensitivity to TMZ is increased in combination with PARP inhibitors in cell lines and xenografts both *in vitro* and *in vivo* (Smith et al. 2015, Tentori et al. 2003, Palma et al. 2009, Gill et al. 2015b, Delaney 2000, Jagtap and Szabó 2005, Tentori et al. 2001a, Tentori et al. 2001b, Calabrese et al. 2004, Curtin et al. 2004). Furthermore, the PARP inhibitor, veliparib, reverses TMZ resistance in multiple xenografts of various tumor types (Palma et al. 2009). As stated above the base excision repair pathway is an important pathway for demethylation, however the increased TMZ sensitivity with PARP inhibitors is likely multifactorial (Jagtap and Szabó 2005, Boulton et al. 1995). For example, stalled replication forks are typically overcome by HR DNA repair, but PARP inhibitors can delay the initiation of this HR-mediated recovery (Cimprich and Cortez 2008, Yang et al. 2004, Lavin 2008). In addition, PARP trapping appears to be critical for improving TMZ sensitivity, which makes olaparib an ideal PARP inhibitor to use in combination with TMZ (Murai et al. 2014b, Pommier, O'Connor and de Bono 2016, Murai et al. 2012a). The combination of TMZ with PARP inhibitors has gained traction with multiple ongoing clinical trials evaluating various combination in multiple diseases (NCT00687765, NCT0215982, NCT01390571, NCT02116777, NCT01858168 and others) (Ohmoto and Yachida 2017) and specifically the TMZ olaparib combination has been deemed safe and worthy of further evaluation in both GBM and small cell lung cancer in various dosing schemes (Farago et al. 2018, Fulton et al. 2017, Halford et al. 2017).

Temozolomide has activity in the relapsed / refractory setting for CRC, likely related to the high prevalence of MGMT promoter hypermethylation in this disease, which is supported by prospective clinical trials. Based on TMZ resistance mechanisms described, preliminary data suggests the addition of PARP inhibitors can lead to a sustained anti-tumor response and appropriate safety data to support this combination is available. Therefore we propose a biomarker driven, open-label clinical trial with TMZ in combination with the poly ADP ribose polymerase (PARP) inhibitor olaparib for MGMT promoter hypermethylated CRC.

Table 2. Objectives and endpoints:

Primary objectives:	Endpoints/variables:
To determine the efficacy of TMZ in combination with olaparib in subjects with MGMT promoter hypermethylated advanced colorectal cancer by the overall response rate (ORR)	ORR by RECIST v1.1 criteria

Secondary objectives:	Endpoints/variables:
To determine the safety of TMZ in combination with olaparib	Rate of \geq grade 3 adverse events by CTCAE v5.0
To estimate the progression free survival (PFS)	PFS
To estimate overall survival (OS)	OS
Exploratory objectives:	Endpoints/variables:
Characterize NGS profiling, patterns of DNA methylation, gene expression, and develop MGMT expression assays	Association of NGS profiling, patterns of DNA methylation, gene expression, and develop MGMT expression assays with efficacy and clinical parameters.
Correlate molecular features with γ H2AX with response	Association of γ H2AX with response rate and survival endpoints
Establish organoids for MGMT promoter hypermethylated colorectal cancer	Form a library of colorectal cancer organoids

Overall design:

This is a Phase II, non-randomized, open-label, single-institution study to evaluate temozolomide in combination with olaparib in patients with MGMT promoter hypermethylated advanced colorectal cancer. Potentially eligible patients will be tested for MGMT promoter hypermethylation by methylation specific PCR after signing a pre-screening consent. The study will begin with a safety evaluation period to assess for dose limiting toxicity (DLT) in the first 6 treated patients, and if toxicity is observed a dose de-escalation schema will be considered.

Study period:

Estimated Date of First Patient Enrolled: January 2020

Estimated Date of Last Patient Completed: January 2022

Number of patients:

The study will enroll 30 patients to receive temozolomide + olaparib combination therapy every 3 weeks (q3w). Patients will provide a tumor tissue sample at screening to determine MGMT promoter hypermethylation by methylation-specific polymerase chain reaction (PCR) analysis.

Treatments and treatment duration:

Systemic therapy:

Temozolomide + Olaparib: Temozolomide (75 mg/m² orally on days 1-7 every 3 weeks) + Olaparib (150 mg orally twice daily days 1-21) in a 21-day cycle.

Duration of treatment:

Treatment will continue until disease progression, unacceptable adverse event(s), withdrawal of consent or death.

Progression during treatment:

During the treatment period, patients who have Response Evaluation Criteria in Solid Tumors, version 1.1 (RECIST 1.1) defined radiological progression will proceed to follow-up. Patients with equivocal progression who are clinically stable may continue on treatment phase of the study at the discretion of the patient and Investigator until progression is confirmed, no earlier than 4 weeks after and preferably within 4 to 6 weeks after the prior assessment of progression of disease.

Follow-up of patients post discontinuation of study drug:

Patients who have discontinued study treatment due to toxicity or symptomatic deterioration, clinical progression/recurrence, or who have commenced subsequent anticancer therapy will be followed until RECIST 1.1-defined progression of disease and then at least for an additional 8 weeks with at least 1 additional follow up scan or death (whichever comes first). A repeat optional tumor biopsy will be done at the time of disease progression unless it is deemed clinically unsafe to perform.

Survival:

All patients in the study should be followed up for survival.

Independent data monitoring committee:

The principal investigator and Yale Center for Clinical Investigation (YCCI) are responsible for monitoring the performance of the study. The Yale Cancer Center Data and Safety Monitoring Committee (DSMC) will provide primary oversight of data and safety monitoring. The Yale DSMC will review and monitor compliance, toxicity and deviations from this study. The committee is composed of clinical specialists with experience in oncology and who have no direct relationship with the study. Information that raises any questions about participant safety will be addressed with the Principal Investigator. The DSMC will review this protocol at a minimum of once every six months.

Statistical methods

We anticipate about 20% of those screened will exhibit an appropriate biomarker as well as meet eligibility criteria. To obtain 30 eligible patients, the mean number of patients to be screened is 150. Using the negative binomial distribution as reference, there is a 6% probability more than 190 subjects will need to be screened to attain the 30 eligible patients.

The primary endpoint is the objective response rate to the combined therapy and will be assessed in a Simon's two-stage optimal design. Published, historical records anticipate a response rate of 5% or lower and we will assume a null hypothesis of 5%. We will reject this null hypothesis in favor of a higher rate if we observe 4 or more responses in the evaluable patient sample of 30. The trial will terminate early if we do not observe 1 or more responses in the first 9 evaluable patients. The probability of 4 or more responses in a sample of 30 is .049, which is the significance level. If the true, underlying response rate is 25% or greater, then this trial has a power of 90%. The expected sample size is 17 under the null hypothesis. There is a 63% chance of stopping early under the null hypothesis.

Secondary endpoints include overall survival, progression-free survival and toxicity. Survival endpoints will be plotted using the Kaplan-Meier, product-limit method and compared across clinical measurements using Cox proportional hazards regression. Time to progression begins at the time of initial treatment and ends at the earliest of withdrawal, diagnosed progression, or death. Toxicity rates will be compared to established rates for these treatments and summarized using means and 95% confidence intervals. Genetic markers will be plotted using heat-maps and statistically compared across responders and nonresponders using the Benjamini-Hochberg correction for multiplicity of p-values.

